#### **10.4.4 Supportive analyses**

Event rates will be compared between treatment groups using the Cochran-Mantel-Haenszel test, stratified by induction therapy.

A logistic regression analysis of the primary efficacy variable will be performed. The odds ratio for treatments, 95% confidence interval for the odds ratio, and p-values (if applicable) will be reported based on the fitted model.

A Kaplan-Meier survival analysis will be performed where all treated BPARs, graft losses, deaths or losses to follow-up that occur up to month 24 will be considered efficacy failures. The incidence of the composite efficacy failure (treated BPAR, graft loss, death or loss to follow-up) within 24 months will be compared between the two treatment groups using Kaplan-Meier probability estimates of efficacy failure and the associated 95% CI obtained

using the standard error derived by applying Greenwood's formula. The differences between the curves will be tested using the log-rank test.

## **10.5 Analysis of secondary objectives**

### **10.5.1 Efficacy (secondary)**

Secondary efficacy variables include:

- The incidence of treated BPAR at 24 months
- The incidence of graft loss at 24 months
- The incidence of death or loss to follow-up at 24 months

The incidence of treated BPAR, graft loss, and death or loss to follow-up will be analyzed using a Cochran-Mantel-Haenszel test stratified by induction therapy.

A Kaplan-Meier survival analysis will be performed for each time to treated BPAR, time to graft loss and time to death or loss to follow-up. The incidences will be compared among the three treatment groups using Kaplan-Meier probability estimates of efficacy failure and the associated 95 % CI obtained using the standard error derived by applying Greenwood's formula. The differences between the curves will be tested using the log-rank test.

FAS will be used for analyses of the secondary efficacy variables.

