#### **10.4.3 Handling of missing values/censoring/discontinuations**

All efforts will be made to complete data except for cases of loss to follow-up, graft loss or death. Loss to follow-up, graft loss or death is defined as one whose last day of contact is prior to Month 24 and who did not experience graft loss or death. The missing data will be assumed to be missing at random except for above cases. The sensitivity analysis based on a complete case analysis and a missing data analysis will be conducted if imputed data exceeds 5 % of total data.

The modified last observation carried forward (LOCF) will be applied if eGFR has not been obtained at study visits. Only in cases where the observed measurement was obtained within 6 weeks of the expected study visit, modified LOCF will be employed to impute missing data. In other words, missing data will be replaced with data from out-of-window visit occur within 6 weeks of scheduled visit. None of data will be carried forward beyond 6 weeks, and will not be imputed by other methods. For the FAS analysis, this will be done regardless of whether a patient discontinued study medication or not. For patients experiencing graft loss, the last value before dialysis or re-transplantation will be used.

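### Section 10.5.1 takes the incidence of treated BPAR and of graft loss from single-event Kaplan-Meier curves, which overstate it, usually modestly, when an event follows a death or (for BPAR) a graft loss

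*Combined protocol and SAP*

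**What the plan says.** Section 10.5.1 lists the 24-month incidences of treated BPAR, of graft loss, and of death or loss to follow-up as secondary efficacy variables. Two analyses follow.

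- The incidences "will be analyzed using a Cochran-Mantel-Haenszel test stratified by induction therapy".
- Separate time-to-event curves are also planned: "A Kaplan-Meier survival analysis will be performed for each time to treated BPAR, time to graft loss"; a third curve covers the remaining component. The quantity read from these curves is stated: "The incidences will be compared among the three treatment groups using Kaplan-Meier probability estimates of efficacy failure", with 95% intervals from Greenwood's formula. Then: "The differences between the curves will be tested using the log-rank test".

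The analysis set is the FAS ("FAS will be used for analyses of the secondary efficacy variables"). The synopsis and Section 10.7 add Fisher's exact test for the composite and each component.

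Section 10.4.3 has censoring in its title but gives no censoring rule for the component curves. After naming loss to follow-up, graft loss and death, it says: "The missing data will be assumed to be missing at random except for above cases". By contrast, the composite Kaplan-Meier analysis in Section 10.4.4 is explicit. Treated BPARs and graft losses count there, and "deaths or losses to follow-up that occur up to month 24 will be considered efficacy failures". The plan mentions no competing risk or cumulative incidence function.

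**The concern.** A patient who dies or loses the graft without rejection can no longer have treated BPAR in that graft. A patient who dies with a working graft can no longer lose it. A single-event Kaplan-Meier curve removes such patients as if they could still have the event, and shares their weight among those left at risk. One minus Kaplan-Meier then describes a setting in which the competing event does not occur. It is not the proportion of patients who have the event by Month 24, which is what the plan names as its variable.

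Two features make the required order of events plausible. Section 1 argues that these kidneys need more protection because their pathology is suboptimal, so graft loss is a realistic competing event. Sections 6.5.8 and 7.4.3 schedule biopsies at Months 3, 12 and 24, so some rejections may be found late.

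At stake are the reported incidence estimates, their intervals and the differences between arms read from them. The plan would also give two figures for one named incidence: a crude proportion behind the Cochran-Mantel-Haenszel test and a Kaplan-Meier figure at or above it. If a later trial is planned from the pilot's rates, the higher figure could carry over.

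**Working it through.** **Inputs from the documents.** Three arms, 24 months of follow-up, 16 per arm. The arm size reproduces from Section 10.6: 12/(1 - 0.20) = 15 per arm; 3 × 15 = 45; the next multiple of the block size 12 is 48, or 16 per arm.

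**Inputs assumed.** All event and competing-event rates and counts below are assumptions, because the documents give none.

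**1. Constant hazards over 24 months.** Let p1 be the true cumulative incidence of the event and p2 that of the competing event. The total cumulative hazard is H = -ln(1 - p1 - p2), and the event's share is H1 = H × p1/(p1 + p2). Hence

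1 - KM = 1 - exp(-H1) = 1 - (1 - p1 - p2)^(p1/(p1 + p2)).

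For p1 = 0.20 and p2 = 0.05: 1 - 0.75^0.8 = 20.6%. For p1 = 0.20 and p2 = 0.30: 1 - 0.50^0.4 = 24.2%.

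| True incidence | Competing 5% | 10% | 20% | 30% |
|---|---|---|---|---|
| 10% | 10.3% | 10.6% | 11.2% | 12.0% |
| 20% | 20.6% | 21.2% | 22.5% | 24.2% |
| 30% | 30.9% | 31.8% | 34.0% | 36.8% |

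At a true 20%, the excess is 0.6 to 4.2 points. With both incidences ranging from 5% to 30%, it is about 0.1 to 6.8 points.

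**2. Two arms with the same true 20%.** The spurious difference is 0.6 points for competing incidences of 5% v 10%, 2.0 points for 5% v 20%, and 3.1 points for 10% v 30%.

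**3. Counts in one arm of 16, with complete follow-up.** Aalen-Johansen then equals the crude proportion.

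Three treated BPARs, crude 3/16 = 18.75%:
- one competing event before all three: 1 - 12/15 = 20.0%
- two before: 1 - 11/14 = 21.4%
- three before: 1 - 10/13 = 23.1%
- any number after all three: 1 - 13/16 = 18.75%, no excess

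Three before is the least favourable order. The same counts under constant hazards give 1 - 0.625^0.5 = 20.9%, an excess of 2.2 points instead of 4.3.

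Two rejections, three competing events, then two rejections: 1 - (14/16)(9/11) = 28.4%, against 4/16 = 25.0%. An arm with four rejections and no competing event gives 25.0%, so the apparent gap is 3.4 points.

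Two graft losses, crude 2/16 = 12.5%: one earlier death gives 1 - 13/15 = 13.3%, and two give 1 - 12/14 = 14.3%.

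**4. Sampling error.** At 20% and n = 16, SE = √(0.2 × 0.8/16) = 0.10. For a difference between two arms, √(2 × 0.2 × 0.8/16) = 0.14. The 0.6 to 4.2 point excess is about 0.06 to 0.42 of one arm's standard error. The largest difference in step 2 is 3.1/14, about 0.2 standard errors.

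**The case against.** The strongest case on the other side has four parts.

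- **Other analyses of these components are free of this bias.** The stratified Cochran-Mantel-Haenszel test in Section 10.5.1 and Fisher's exact test use crude proportions. Section 6.5.8 has patients followed to Month 24 after stopping study drug, so those proportions suffer only from loss to follow-up. This stands.
- **The log-rank test is sound.** A reader might infer that competing events make it invalid and that Gray's test must replace it. The documents do not support that. Censoring competing events gives a legitimate comparison of cause-specific hazards, and which test should lead depends on the question asked.
- **The bias is conditional and small.** A reader might infer that an arm with more deaths or graft losses must show an inflated rejection rate. It need not: if those events come after the rejections, there is no excess. The sizes above rest on assumed rates, and no conclusion at 16 per arm would plausibly turn on them. This stands, and it limits the weight of the point.
- **The documents never say that death or graft loss is censored.** True. It is an inference from a single-event method with no other rule stated. If another rule is meant, it should be written down.

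None of this defends one minus Kaplan-Meier as the stated estimator of incidence.

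**Conclusion.** The point holds for the Kaplan-Meier incidence estimates of treated BPAR and graft loss and for their confidence intervals. If death, and graft loss for BPAR, are censored, the estimates are too high whenever an event of interest follows a competing event. The excess is unequal between arms if competing events differ in number or timing.

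At an assumed true incidence of 20% with constant hazards, it is about 0.6 to 4.2 points for competing incidences of 5% to 30%, and zero if all competing events come last. That is small beside a standard error of about 10 points per arm. The reason to act is that the error has a known direction and is easy to avoid.

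The point should not be stretched to the composite curve in Section 10.4.4, where death and graft loss are themselves failures. Nor is loss to follow-up a competing event for these two components: it is ordinary censoring.

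**What to change.** In Section 10.5.1:

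- Replace the Kaplan-Meier incidence estimates for treated BPAR and graft loss by Aalen-Johansen cumulative incidence, with 95% intervals from the matching variance estimator in place of Greenwood's formula.
- Name the competing events: death and graft loss for treated BPAR; death for graft loss. State that loss to follow-up is censored for both.
- Keep the log-rank test, labelled as a comparison of cause-specific hazards. Gray's test is optional.
- Leave the Cochran-Mantel-Haenszel and Fisher tests and the composite Kaplan-Meier analysis unchanged.

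The cost is a few lines of analysis text and a standard software routine. No new data are needed, because rejection, biopsy, graft loss and death are already recorded under Sections 7.4.1 to 7.4.5.

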### 6.3 Treatment Assignment

Once a potential study patient is identified and he/she fulfills the inclusion/exclusion criteria and the informed consent form is signed, the patient will be entered into the study.

The patient will be assigned a patient identification number sequentially ( 001, 002 etc) Randomization will be performed by the Principal Investigator and/or the clinical research

coordinator using randomization envelopes which each have been randomly assigned a treatment group. A total of 16 patients will be randomized into each treatment group.

If a patient fulfills the conditions to be randomized, the study team will notify Research Pharmacy staff with the treatment arm and a subject ID number. The Research Pharmacy will then dispense the assigned drug accordingly.

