#### **10.6 Sample size calculation**

Since this is a pilot study, the sample size estimation method proposed by Julious was considered in order to minimize the sample size (14). Julious proposes to employ sample size of 12 per group for a pilot study (14). Assuming the drop out rate of 20% along with the ease of blocked randomization, we propose the sample size of 16 per arm, totaling 48 patients. The estimated effect size,  $\alpha$ , and  $\beta$  corresponding to this sample size are 0.9, 0.05 (two-sided), and 0.2 respectively (15). A block size of 12 along with an allocation ratio of 1:1:1 will be employed as a randomization scheme.

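### With 16 patients per arm, a Greenwood-based 95% interval collapses to a point, or is undefined, in any arm with no events, and Sections 10.4.4 and 10.5.1 state no scale and no zero-event rule

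*Combined protocol and SAP*

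**What the plan says.** Section 10.5.1 covers the three component endpoints: "A Kaplan-Meier survival analysis will be performed for each time to treated BPAR, time to graft loss and time to death or loss to follow-up". Each comparison uses Kaplan-Meier probability estimates with a 95% interval "obtained using the standard error derived by applying Greenwood's formula". Section 10.4.4 gives the composite the same treatment. Neither section says whether the interval is formed on the plain, log or log-log scale, or what to report for an arm with no events.

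Section 10.4.4 also plans a logistic regression, for the primary composite only: "The odds ratio for treatments, 95% confidence interval for the odds ratio, and p-values (if applicable) will be reported based on the fitted model". It names no penalised or exact alternative.

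On size, Section 6.3 states: "A total of 16 patients will be randomized into each treatment group". Section 10.6 gives the same figure: "we propose the sample size of 16 per arm, totaling 48 patients".

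The synopsis and Section 10.7 name Fisher's exact test for the composite and each component. That supplies a p-value, not an interval around an event rate. The documents give no expected event rate for any of these endpoints.

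**The concern.** One main use of a pilot is to report event rates with intervals that show how uncertain they are. The Greenwood standard error is a large-sample formula, and it reports no uncertainty at all when nothing has happened in an arm. An arm with 0 graft losses in 16 patients would be shown with an interval of 0 to 0%, although the data are compatible with a true rate of up to about 20%. Someone planning the next trial, or judging whether graft loss is acceptably rare, would be misled about what the pilot has ruled out. The logistic model for the composite has a related weakness: if an arm has no failures, its odds ratio has no finite maximum-likelihood estimate.

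**Working it through.** **Planned arm size.** Section 10.6 starts from 12 per group and allows for 20% dropout. 12 / 0.80 = 15 per arm, or 45 in total. The next multiple of the block size of 12 is 48, or 16 per arm. The plan's figure reproduces, so n = 16 is used below.

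**Zero events.** Greenwood's variance is S² × Σ d/[r(r − d)], where S is the Kaplan-Meier survival estimate, d the events and r the number at risk at each event time. With no events every d is 0, so the variance is 0 whether or not patients are censored.
- Plain scale: 0 ± 1.96 × 0, an interval of 0 to 0%.
- Log-log scale: needs log(−log S) at S = 1, which is log 0 and undefined.
- Exact (Clopper-Pearson) upper limit for 0/16: 1 − 0.025^(1/16) = 20.6%.

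**One or more events, no censoring.** Greenwood's variance reduces to p(1 − p)/n. For 1/16, the SE is √(0.0625 × 0.9375 / 16) = 0.0605, and the plain interval is 0.0625 ± 1.96 × 0.0605, or −5.6% to 18.1%. The other rows follow in the same way:

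| Events of 16 | Plain Greenwood | Log-log Greenwood | Clopper-Pearson |
|---|---|---|---|
| 0 | 0 to 0% | undefined | 0 to 20.6% |
| 1 | −5.6 to 18.1% | 0.9 to 36.8% | 0.2 to 30.2% |
| 2 | −3.7 to 28.7% | 3.3 to 41.4% | 1.6 to 38.3% |
| 3 | −0.4 to 37.9% | 6.5 to 47.5% | 4.0 to 45.6% |
| 4 | 3.8 to 46.2% | 10.2 to 53.7% | 7.3 to 52.4% |

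Negative lower limits arise only on the plain scale, and only at 1 to 3 events.

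**How often.** The true rates here are assumptions, taken as equal in all arms. The chance that a given arm has no events is (1 − p)^16, and the chance that at least one of three arms has none is 1 − [1 − (1 − p)^16]³. Coverage is the exact binomial sum over all outcomes at n = 16 without censoring.

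| Assumed 24-month rate | At least one arm with no events | Plain interval: coverage | Log-log with exact limit at 0 events: coverage |
|---|---|---|---|
| 5% | 82% | 56% | 96% |
| 10% | 46% | 81% | 93% |
| 15% | 21% | 92% | 98% |
| 20% | 8% | 85% | 97% |
| 25% | 3% | 91% | 96% |

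The plain interval misses mostly because its upper limit is too low: that limit falls below the true rate in 44%, 19% and 14% of samples at 5%, 10% and 20%.

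**Logistic model for the composite.** At 0/16 against 4/16, the maximum-likelihood odds ratio goes to 0 with an interval of 0 to infinity. Firth's method gives 0.08 (0.0006 to 0.90), and the exact method gives 0 (0 to 1.39). At 1/16 against 3/16, maximum likelihood gives 0.29 (0.03 to 3.13), an ordinary finite result. The model therefore fails only if an arm has no failures (or only failures). The chance of at least one arm without failures is 46% at a composite rate of 10%, 8% at 20%, 3% at 25% and 1% at 30%.

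**Deaths in the component curves.** Suppose 2 of 16 patients have the event and deaths before those events are censored. With one death, one minus Kaplan-Meier is 2/15 = 13.3%; with two, 2/14 = 14.3%. The cumulative incidence is 2/16 = 12.5% in both cases. The excess is 0.8 or 1.8 percentage points, small beside intervals more than 30 points wide.

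**The case against.** The strongest reply is that the plan names a standard error and not a scale. Log-log intervals use the same standard error, and with at least one event they stay between 0 and 100%. Their upper limits at 1 to 3 events are above the Clopper-Pearson limits, not below them. A reader might infer that the planned intervals will have negative limits and cover far below 95%. The documents do not support that as a fact, because it holds only if the interval is left untransformed. The zero-event case stands on either scale.

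Second, event rates are not given. Death is analysed only together with loss to follow-up, and Section 10.6 assumes 20% dropout, or 0.20 × 16 = 3.2 patients per arm, although not every dropout is lost to follow-up. The composite adds rejection and graft loss, so an empty arm is less likely there. This stands, and it confines the problem mainly to rare components.

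Third, a reader might infer that the logistic odds ratios for graft loss, death or rejection will be zero-width or negative. No such models are planned. Logistic regression is for the composite only, and it fails through an unbounded interval.

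Fourth, these are supportive and secondary analyses, and Fisher's exact test is already named. Graft loss and death are also reported as serious adverse events with counts, so 0/16 would be visible, and no stated decision rule uses these intervals. All of that limits the consequence, but none of it supplies a valid interval.

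**Conclusion.** The point holds, with limits. The specified method gives a wrong or undefined interval in any arm of 16 with no events, where the exact interval runs to 20.6%. No choice of scale repairs this, and it does not depend on the amount of censoring.

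How often it would happen rests on assumed rates: at least one of three arms is affected with probability 82% at 5%, falling to 8% at 20%. The coverage shortfall at 1 or more events rests on two further assumptions, an untransformed interval and no censoring.

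The same formula applies to all three arms, so a reader should not infer that it specifically understates harm under everolimus. Nor do the documents support a claim that Kaplan-Meier materially overstates rejection or graft loss: the handling of deaths is not stated, and the bias is small when deaths are few. The weakness in the logistic model is real but unlikely if the composite rate is about 20% or more.

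**What to change.** In Sections 10.4.4 and 10.5.1, state that Kaplan-Meier 95% intervals are formed on the log-log scale. For an arm with no events, use an exact limit: Clopper-Pearson if no patient is censored before the time point, beta-product if some are. Exact-type intervals throughout would serve equally well.

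In Section 10.4.4, add that if an arm has no composite failures, or only failures, the odds ratio and its interval will come from Firth or exact logistic regression. Name one of the two in advance, because in the 0/16 against 4/16 example they differ on whether the interval includes 1.

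State how deaths are handled in the curves for treated BPAR and graft loss. Cumulative incidence with death as a competing event is an option, not a necessity.

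The cost is a few sentences and standard software, with no new data, patients or design change. The downside is somewhat wider intervals, and slightly conservative ones if exact limits are used throughout: Clopper-Pearson covers 98 to 99% at true rates of 5%, 10% and 20%.

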### **10.5.2 Safety**

Safety variables to be assessed include discontinuation from study, discontinuation from treatment, renal function, AE/infection, SAE, notable events, laboratory tests, and vital signs.

Comparison of calculated GFR using an analysis of covariance (ANCOVA) with baseline (Month 1) GFR as a covariate, and treatment and induction therapy as main effects, will be performed. Month 24 GFRs will be divided into three categories (<30, 30-60, >60) to classify chronic kidney disease. The proportion of patients in certain categories will be compared between treatment groups using the Cochran-Mantel-Haenszel test controlling for the Month 1 category.

Other safety variables include incidences of AEs, SAEs, new onset diabetes mellitus, CMV, BKV and proteinuria. These incidences will be compared between treatment groups using a Cochran-Mantel-Haenszel test, stratified by induction therapy. Urine protein/creatinine ratios will be compared between treatment groups using the Wilcoxon Rank-Sum test.

Additional assessments of safety will be based on the frequency of adverse events and on the number of laboratory values that fall outside of pre-determined notable ranges. Other safety data (e.g. vital signs and special tests) will be considered as appropriate. The data collected will be presented in listings, summary tables and graphs. All analyses will be performed on the SS.

Adverse events will be summarized by presenting, for each treatment group, the number and percentage of patients having any adverse event, having an adverse event in each body system and having each individual adverse event. The same type of summaries will be provided for serious adverse events and for events suspected to be related to the study medication. Any other information collected (e.g. severity or relatedness to study medication) will be listed as appropriate.

Laboratory data will be summarized by presenting shift tables using notable ranges (baseline to most extreme post-baseline value), by presenting summary statistics of raw data and change from baseline values (means, medians, standard deviations, ranges) and by the flagging of notable values in data listings.

Data from other tests (e.g. vital signs) will be listed, notable values will be flagged, and any other information collected will be listed as appropriate. Any statistical tests performed to explore the data will be used only to highlight any interesting comparisons that may warrant further consideration. The data collected will be presented in listings, summary tables and graphs. All analyses will be performed on the SS.

